#### 4.1.2 Immunogenicity Assessment Methods

Anti-HA antibody titers will be measured using the HAI method from the sera obtained on D0 and D28 after the last vaccinationa, according to a reference technique. For each vaccine strain, samples obtained pre- and post-vaccination from a same subject will be tested simultaneously in

a D56 for subjects aged 6 months to 8 years, and D28 for subjects aged 9 years and older

**450 – Quadrivalent Influenza Vaccine**

---

duplicates. The titer assigned at the time of the statistical analysis to each sample will be the GM of 2 independent determinations.

Additional analyses may be performed on the blood samples if required by the Sponsor to obtain further influenza antibody titration. In such a case, these analyses will not require additional blood samplings.

***Anti-Influenza Virus Antibody Titration by Inhibition of Hemagglutination***

Assays will be performed by the Sponsor's laboratory (GCI, Swiftwater, PA, USA) or at a contract research organization laboratory under GCI responsibility. The address is provided in the Operating Guidelines.

Test serum samples and quality control sera are incubated with Neuraminidase to eliminate non-specific inhibitors. Adsorption of spontaneous anti-species agglutinins is then performed by incubating the serum samples and quality control sera with a red blood cell (RBC) suspension. The mixtures are then centrifuged and the supernatants containing the treated sera are collected for testing.

Ten two-fold dilutions of the initial 1/10 dilution of the treated serum samples and quality control sera are incubated with previously titrated HA antigen (4 hemagglutination units [HAU]/25 µL). HA antigen is not added to serum control wells containing only serum and RBCs. The mixture is then incubated and a RBC suspension is added. Following incubation, the results are read. The serum titer against each influenza strain tested is determined as the reciprocal of the highest dilution that exhibits complete inhibition of hemagglutination. Each serum sample is titrated in independent duplicates and the two values, which cannot differ by more than a two-fold dilution, are reported. The lower limit of quantitation (LLOQ) is set at the reciprocal of the lowest dilution used in the assay, i.e., 10 (1/dil). Titers below this level are reported as <10 (1/dil). The upper limit of quantitation (ULOQ) is 10240 (1/dil). Titers above this level are reported as ≥ 10240 (1/dil).

**4.2 Safety Endpoints and Assessment Methods**

See Section 9.2 of the protocol.

**4.2.1 Safety Definitions**

The following definitions are taken from the International Conference on Harmonisation (ICH) E2A Guideline for Clinical Safety Data Management: Definitions and Standards for Expedited Reporting.

***Adverse Event (AE):***

An AE is any untoward medical occurrence in a patient or clinical investigation subject administered a pharmaceutical product and which does not necessarily have to have a causal relationship with this treatment. An AE can therefore be any unfavorable and unintended sign (including an abnormal laboratory finding, for example), symptom or disease temporally associated with the use of a medicinal product, whether or not considered related to the medicinal product.

**450 – Quadrivalent Influenza Vaccine**

---

Therefore an AE may be:

A new illness

The worsening of a concomitant illness

An effect of the vaccination, including the comparator

A combination of the above

All AEs include serious and non-serious AEs.

Surgical procedures are not AEs; they are the action taken to treat a medical condition. It is the condition leading to the action taken that is the AE (if it occurs during the trial period).

Pre-existing medical conditions are not to be reported as AEs. However, if a pre-existing condition worsens in frequency or intensity, or if in the assessment of the treating physician there is a change in its clinical significance, this change should be reported as an AE (exacerbation). This applies equally to recurring episodes of pre-existing conditions (e.g., asthma) if the frequency or intensity increases post-vaccination.

***Serious Adverse Event (SAE):***

*Serious* and *severe* are not synonymous. The term *severe* is often used to describe the intensity of a specific event as corresponding to Grade 3. This is not the same as *serious* which is based on patient / event outcome or action criteria usually associated with events that pose a threat to a patient's life or functioning. Seriousness, not severity, serves as a guide for defining regulatory reporting obligations.

An SAE is any untoward medical occurrence that at any dose:

Results in death

Is life-threateninga

Requires inpatient hospitalization or prolongation of existing hospitalizationb

Results in persistent or significant disability / incapacityc

Is a congenital anomaly / birth defect

Is an important medical eventd

---

a The term "life-threatening" refers to an event in which the subject was at risk of death at the time of the event; it does not refer to an event which hypothetically might have caused death if it were more severe.

b All medical events leading to hospitalizations will be recorded and reported as SAEs, with the exception of: hospitalization planned before inclusion into the study or out-patient treatment with no hospitalization.

c "Persistent or significant disability or incapacity" means that there is a substantial disruption of a person's ability to carry out normal life functions.

d Medical and scientific judgment should be exercised in deciding whether expedited reporting is appropriate in other situations, such as important medical events that may not be immediately life-threatening or result in death or hospitalization but may jeopardize the health of the subject or may require intervention to prevent one of the

**450 – Quadrivalent Influenza Vaccine**

---

Additionally, AESIs listed in Section 4.3.1.4.6 are to be considered as SAEs.

***Adverse Reaction:***

All noxious and unintended responses to a medicinal product related to any dose should be considered adverse reactions (AR).

(The phrase “responses to a medicinal product” means that a causal relationship between a medicinal product and an AE is at least a reasonable possibility)

***Unexpected Adverse Reaction:***

An unexpected adverse reaction is an AR, the nature or severity of which is not consistent with the applicable product information (e.g., Investigator’s Brochure for an unapproved investigational medicinal product).

The following additional definitions are used by Sanofi Pasteur:

***Solicited Reaction:***

A solicited reaction is an AE that is prelisted in the CRF. The assessment of these AEs post-vaccination is mandatory. A solicited reaction is defined by a combination of:

Symptom and

Onset post-vaccination

e.g., injection site swelling between D0 and D7 post-vaccination, or fever between D0 and D7.

A solicited reaction is therefore an AR observed and reported under the conditions (symptom and onset) prelisted (i.e., solicited) in the CRF and considered as related to vaccination.

***Unsolicited AE / AR:***

An unsolicited AE is an observed AE that does not fulfill the conditions prelisted in the CRF in terms of diagnosis and / or onset post-vaccination, i.e., excluding solicited reactions, e.g., if fever between D0 and D7 is a solicited reaction (i.e., prelisted in the CRF), then a fever starting on D7 is a solicited reaction, whereas fever starting on D8 post-vaccination is an unsolicited AE.

An unsolicited non-serious AE is an unsolicited AE excluding SAEs.

***Injection Site Reaction:***

An injection site reactiona is an AR at and around the injection site. Injection site reactions are commonly inflammatory reactions.

---

other outcomes listed in the definition above. These should also usually be considered serious. Examples of such events include allergic bronchospasm requiring intensive treatment in an emergency room or at home, blood dyscrasias or convulsions that do not result in inpatient hospitalization, or the development of drug dependency or drug abuse, new onset diabetes or autoimmune disease.

a All injection site AEs are considered to be related to vaccination and are therefore all *injection site reactions*.

***Systemic AE:***

Systemic AEs are all AEs that are not injection site reactions. They therefore include systemic manifestations such as headache, fever, as well as localized or topical manifestations that are not associated with the vaccination site, e.g., erythema that is localized but that is not at the injection site.

***Adverse Events of Special Interest (AESIs):***

AESIs are AEs that are considered by the Sponsor to be relevant for the monitoring of the safety profile of the investigational vaccine (see Section 4.3.1.4.6).

**4.2.2 Safety Endpoints**

The endpoints for the evaluation of safety are:

- Occurrence of unsolicited AEs reported in the 30 minutes after each / any injection
- Occurrence of solicited (prelisted in the subject diary card (DC) and CRF) injection site reactions and systemic reactions within 7 days following each / any injection
- Occurrence of unsolicited (spontaneously reported) AEs within 28 days following each / any injection
- Occurrence of SAEs (including AESIs) throughout the trial (i.e., from D0 through end of the study)

Depending on the item, endpoints described include: nature (Medical Dictionary for Regulatory Activities [MedDRA] preferred term), time of onset, duration, number of days of occurrence, Grade of severity, relationship to vaccine, whether the AE led to early termination from the study, seriousness, or outcome.

**4.2.3 Safety Assessment Methods**

At Visit 2 (subjects aged 9 or older) or at Visit 2 and Visit 3 (subjects aged 6 months to 8 years), the Investigator or a delegate will perform a clinical or medically-driven physical examination, and will ask the subjects / parents / legally acceptable representatives about any solicited reactions and unsolicited AEs recorded in the DC, as well as about any other AEs that may have occurred since the previous visit. All relevant data will be transcribed into the CRF according to the instructions provided by the Sponsor.

**4.2.3.1 Immediate Post-vaccination Surveillance Period**

Subjects will be kept under observation for 30 minutes after vaccination to ensure their safety. Any AE that occurs during this period will be noted on the source document and identified as an immediate event / reaction; and will additionally be recorded in the CRF, as follows:

- Any unsolicited systemic AE occurring during the first 30 minutes post-vaccination will be recorded on the CRF as immediate unsolicited systemic AE
- Solicited and unsolicited injection site reactions and solicited systemic reactions will be recorded and analyzed as starting on the day of vaccination

---

**450 – Quadrivalent Influenza Vaccine**

---

- Any SAE occurring during the first 30 minutes post-vaccination will be reported in the same way as any other SAE and to the Sponsor.

**4.2.3.2 Reactogenicity (Solicited Reactions From Day 0 to Day 7 After the Vaccination)**

After vaccination, subjects / parents / legally acceptable representatives will be provided with a safety DC, a digital thermometer, and a flexible ruler, and will be instructed how to use them. The following items will be recorded by the subjects in the DC on the day of vaccination and for the next 7 days (i.e., D0 to D7) until resolution:

- Daily temperature, with the route by which it was taken
- Daily measurement or intensity grade of all other solicited injection site and systemic reactions
- Action taken for each event, if any (e.g., medication)

The action taken by the subjects / parents or legally acceptable representatives to treat any **solicited reactions** will be classified in the CRF using the following scale:

0: None

1: Medication (self-medication with an existing prescription or over-the-counter medication)

2: Health care provider contact (no new medication prescribed)

3: Health care provider contact and prescription of a new medication (health care provider instructed subject to take a new medication, either an over-the-counter medication or one requiring a written prescription)

4: Hospitalization (inpatient)

Table 4.1, Table 4.2, Table 4.3, Table 4.4 and Table 4.5 present, respectively, the injection site reactions and systemic reactions that are prelisted in the DCs and CRF for the different age group, together with the intensity scales.

**Table 4.1: Solicited injection site reactions: terminology, definitions, and intensity scales for subjects aged 6 to 23 months**

CRF term (MedDRA lowest level term [LLT])	Injection site tenderness	Injection site erythema	Injection site swelling
Diary card term	Tenderness	Redness	Swelling
Definition		Presence of a redness including the approximate point of needle entry	Swelling at or near the injection site Swelling or edema is caused by a fluid infiltration in tissue or cavity and, depending on the space available for the fluid to disperse, swelling may be either soft (typically) or firm (less typical) to touch and thus can be best described by looking at the size of the swelling
Intensity scale*	Grade 1: Minor reaction when injection site is touched Grade 2: Cries or protests when injection site is touched Grade 3: Cries when injected limb is moved, or the movement of the injected limb is reduced	Grade 1: > 0 to < 25 mm Grade 2: ≥ 25 to < 50 mm Grade 3: ≥ 50 mm	Grade 1: > 0 to < 25 mm Grade 2: ≥ 25 to < 50 mm Grade 3: ≥ 50 mm

\* For the subjective reaction of tenderness, parents / legally acceptable representatives will record the intensity level (Grade 1, 2, or 3) in the DC. For the measurable reactions of redness and swelling, they will record just the size of the reaction, and the classification as Grade 1, 2, or 3 will be assigned at the time of the statistical analysis.

**Table 4.2: Solicited injection site reactions: terminology, definitions, and intensity scales for subjects aged 2 to 11 years**

CRF term (MedDRA LLT)	Injection site pain	Injection site erythema	Injection site swelling
DC term	Pain	Redness	Swelling
Definition		Presence of a redness including the approximate point of needle entry	Swelling at or near the injection site Swelling or edema is caused by a fluid infiltration in tissue or cavity and, depending on the space available for the fluid to disperse, swelling may be either soft (typically) or firm (less typical) to touch and thus can be best described by looking at the size of the swelling
Intensity scale* for subjects aged 2 to 11 years	Grade 1: Easily tolerated Grade 2: Sufficiently discomforting to interfere with normal behavior or activities Grade 3: Incapacitating, unable to perform usual activities	Grade 1: >0 to <25 mm Grade 2: ≥25 to <50 mm Grade 3: ≥50 mm	Grade 1: >0 to <25 mm Grade 2: ≥25 to <50 mm Grade 3: ≥50 mm

\* For the subjective reaction of pain, subjects / parents / legally acceptable representatives will record the intensity level (Grade 1, 2, or 3) in the DC. For the measurable reactions of redness and swelling they will record just the size of the reaction, and the classification as Grade 1, 2, or 3 will be assigned at the time of the statistical analysis.

**Table 4.3: Solicited injection site reactions: terminology, definitions, and intensity scales for subjects aged 12 years or older**

CRF term (MedDRA lowest level term [LLT])	Injection site pain	Injection site erythema	Injection site swelling
Diary card term	Pain	Redness	Swelling
Definition		Presence of a redness including the approximate point of needle entry	Swelling at or near the injection site Swelling or edema is caused by a fluid infiltration in tissue or cavity and, depending on the space available for the fluid to disperse, swelling may be either soft (typically) or firm (less typical) to touch and thus can be best described by looking at the size of the swelling
Intensity scale*	Grade 1: No interference with activity Grade 2: Some interference with activity Grade 3: Significant; prevents daily activity	Grade 1: $\geq 25$ to $\leq 50$ mm Grade 2: $\geq 51$ to $\leq 100$ mm Grade 3: $> 100$ mm	Grade 1: $\geq 25$ to $\leq 50$ mm Grade 2: $\geq 51$ to $\leq 100$ mm Grade 3: $> 100$ mm

\* For the subjective reaction of pain, subjects / parents / legally acceptable representatives will record the intensity level (Grade 1, 2, or 3) in the diary card. For the measurable reactions of redness and swelling, they will record just the size of the reaction, and the classification as Grade 1, 2, or 3 will be assigned at the time of the statistical analysis

**Table 4.4: Solicited systemic reactions: terminology, definitions, and intensity scales for subjects aged 6 to 23 months**

CRF term (MedDRA LLT)	Fever	Vomiting	Crying abnormal	Drowsiness	Appetite lost	Irritability
Diary card term	Temperature	Vomiting	Abnormal crying	Drowsiness	Loss of appetite	Irritability
Definition	Elevation of temperature to $\geq 38.0^{\circ}\text{C}$	Vomiting does not include spitting up	Inconsolable crying without a reason	Reduced interest in surroundings, or increased sleeping	See intensity scale	An excessive response to stimuli: increased fussiness, whining, and fretfulness despite attempts to comfort the infant and despite caregiver responses that would normally be soothing
Intensity scale*	Grade 1: $\geq 38.0^{\circ}\text{C}$ to $\leq 38.5^{\circ}\text{C}$ Grade 2: $> 38.5^{\circ}\text{C}$ to $\leq 39.5^{\circ}\text{C}$ Grade 3: $> 39.5^{\circ}\text{C}$	Grade 1: 1 episode per 24 hours Grade 2: 2–5 episodes per 24 hours Grade 3: $\geq 6$ episodes per 24 hours or requiring parenteral hydration	Grade 1: $< 1$ hour Grade 2: 1–3 hours Grade 3: $> 3$ hours	Grade 1: Sleepier than usual or less interested in surroundings Grade 2: Not interested in surroundings or did not wake up for a feed / meal Grade 3: Sleeping most of the time or difficult to wake up	Grade 1: Eating less than normal Grade 2: Missed 1 or 2 feeds / meals completely Grade 3: Refuses $\geq 3$ feeds / meals or refuses most feeds / meals	Grade 1: Easily consolable Grade 2: Requiring increased attention Grade 3: Inconsolable

\* For all reactions but fever, parents / legally acceptable representatives will record the intensity level (Grade 1, 2, or 3) in the DC. For fever, they will record the body temperature, and the classification as Grade 1, 2, or 3 will be assigned at the time of the statistical analysis.

**Table 4.5: Solicited systemic reactions: terminology, definitions, and intensity scales for subjects aged 2 years or older**

CRF term (MedDRA LLT)	Fever	Headache	Malaise	Myalgia	Shivering
DC term	Temperature	Headache	Feeling unwell	Muscle aches and pains	Shivering
Definition	Elevation of temperature to $\geq 38.0^{\circ}\text{C}$	Pain or discomfort in the head or scalp. Does not include migraine.	General ill feeling. Malaise is a generalized feeling of discomfort, illness, or lack of well-being that can be associated with a disease state. It can be accompanied by a sensation of exhaustion or inadequate energy to accomplish usual activities.	Muscle aches and pains are common and can involve more than one muscle at the same time. Muscle pain can also involve the soft tissues that surround muscles. These structures, which are often referred to as connective tissues, include ligaments, tendons, and fascia (thick bands of tendons). Does not apply to muscle pain at the injection site which should be reported as injection site pain.	Cold feeling
Intensity scale*	Grade 1: $\geq 38.0^{\circ}\text{C}$ to $\leq 38.4^{\circ}\text{C}$ Grade 2: $\geq 38.5^{\circ}\text{C}$ to $\leq 38.9^{\circ}\text{C}$ Grade 3: $\geq 39.0^{\circ}\text{C}$	Grade 1: No interference with activity Grade 2: Some interference with activity Grade 3: Significant; prevents daily activity	Grade 1: No interference with activity Grade 2: Some interference with activity Grade 3: Significant; prevents daily activity	Grade 1: No interference with activity Grade 2: Some interference with activity Grade 3: Significant; prevents daily activity	Grade 1: No interference with activity Grade 2: Some interference with activity Grade 3: Significant; prevents daily activity

\* For all reactions but fever, parents / legally acceptable representatives will record the intensity level (Grade 1, 2, or 3) in the DC. For fever, they will record the body temperature, and the classification as Grade 1, 2, or 3 will be assigned at the same time of the statistical analysis.

### 4.3 Derived Endpoints: Calculation Methods

Terms used in the clinical safety tables to describe the safety events are specified below.

AE: adverse event includes immediate, solicited, and unsolicited non-serious or serious event.

AR: adverse reaction corresponds to related AE.

Immediate AE/AR: unsolicited non-serious systemic AE ticked "immediate (within 30 minutes from the vaccination)" by the Investigator in the eCRF or electronic serious adverse event (eSAE) with time to onset within 30 minutes after vaccination with either dose 1 or dose 2.

SR: solicited reactions are events pre-listed in the eCRF, and which occurred during the solicited period (D0 through D7 after vaccination with either dose 1 or dose 2).

Unsolicited AE: AE recorded in the eCRF unsolicited form and eSAE, excluding SRs. Therefore, include immediate AEs.

Unsolicited non-serious injection site reactions are always recorded without relationship and analyzed as ARs.

Unsolicited AEs to be analyzed are AEs which occur between Visit 1 and Visit 2 (and between Visit 2 and Visit 3 for subjects requiring two doses). Unsolicited AEs occurring after the last visit - and which are not SAE - will be presented in separate listings.

SAE: unsolicited AE considered serious by the Investigator.

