**Table 3.1: Table of Study Procedures for Subjects Aged 6 Months to 8 Yearsa**

Phase III Trial, 3 Visits, 2 Vaccinations, 2 Blood Samples

Visit	V01	Phone Call or Home Visit	V02	Phone Call or Home Visit	V03
Trial timelines (days)	D0	V01 + 3 days	V01 + 28 days	V02 + 3 days	V02 + 28 days
Trial windows (days)	-	+2	± 2	+2	± 2
Indicative Months (M)			M1		M2
Informed consent / assent forms signed and dated	X				
Inclusion / exclusion criteria	X				
Demographics	X				
History of seasonal influenza vaccination / history of influenza diagnosis*	X				
Significant medical history	X				
Physical examination	X		X		X
Temperature (axillary)	X		X		
Temporary and definitive contraindications			X		
Assign subject number	X				
Blood sampling (3 mL)	BL1†				BL2
Vaccine injection	VAC1		VAC2		
30-minute surveillance period	X		X		
Diary Card (DC): Provided Collected	DC1		DC2 DC1		DC2
Contact with Subjects‡		X		X	
Recording of solicited injection site & systemic reactions			X		X
Recording of unsolicited non-serious adverse events			X		X
Reportable concomitant medication	X		X		X
Termination record					X
Serious adverse events§	Collected throughout the trial				

a ‘6 months to 8 years’ means from the day of the 6th month after birth to the day before the 9th birthday

- \* History of seasonal influenza vaccination and influenza diagnosis will be collected within the past 3 years or since birth for subjects aged 6 to 35 months
- † Collection of the first blood sample (BL1) will be before vaccination
- ‡ Telephone Calls or Home Visits:: trial personnel will ensure correct completion of DC, ask the subjects / subject's parent(s) / legally acceptable representative(s) whether the subject experienced any SAEs not yet reported, confirm the next visit and remind the subjects / subject's parent(s) / legally acceptable representative(s) that the DC should be brought to the trial center at the next visit
- § Including all AESIs

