**Table 3.2: Table of Study Procedures for Subjects Aged 9 Years or oldera**

Phase III Trial, 2 Visits, 1 Vaccination, 2 Blood Samples

Visit	V01	Phone Call or Home Visit	V02
Trial timelines (days)	D0	Visit 1 + 3 days	Visit 1 + 28 days
Trial windows (days)	-	+2	± 2
Indicative Months (M)			M1

Informed consent / assent forms signed and dated	X		
Inclusion / exclusion criteria	X		
Demographics	X		
History of seasonal influenza vaccination / history of influenza diagnosis*	X		
Significant medical history	X		
Physical examination	X		X
Temperature (axillary)	X		
Urine pregnancy test†	X		
Assign subject number	X		
Blood sampling (3 or 5 mL‡)	BL1§		BL2
Vaccine injection	VAC1		
30-minute surveillance period	X		
Diary Card (DC) Provided Collected	DC1		DC1
Contact with Subjects**		X	
Recording of solicited injection site & systemic reactions			X
Recording of unsolicited non-serious adverse events			X
Reportable concomitant medication	X		X
Termination record			X
Serious adverse events††	Collected throughout the trial		

\* History of seasonal influenza vaccination and influenza diagnosis will be collected within the past 3 years

† For women of childbearing potential, the urine pregnancy test is to be performed before vaccination.

‡ 3 mL for subjects aged 9 to 11 years and 5 mL for subjects aged 12 years or older

a '9 years or older' means from the day of the 9th birthday

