**450 – Quadrivalent Influenza Vaccine**

---

- start date of the unsolicited non-serious AE – date of last vaccination

The time of onset should be considered as missing only if one or both of the dates are missing or partially missing.

The unsolicited non-serious AEs analyzed “Within 28 days” correspond to AEs with a time of onset between 0 and 28 days after vaccination or missing. An AE with missing time of onset will be considered having occurred just after the last vaccination, so will be included in these tables.

Note: Unsolicited non-serious AE that occur before vaccination (negative time of onset) or with a time of onset higher than 28 days will not be included in analysis but will be listed separately.

Time of onset will be displayed as follows:

- D0-D3
- D4-D7
- $\geq$  D8
- Missing

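### Section 4.3 selects unsolicited non-serious AEs by visit interval and Section 4.3.1.2.4 by onset 0 to 28 days; the rules disagree when visits fall off day 28

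*SAP*

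**What the plan says.** Two sections of the SAP state which unsolicited AEs enter the analysis.

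- **Section 4.3 (visit rule).** "Unsolicited AEs to be analyzed are AEs which occur between Visit 1 and Visit 2", extended to Visit 2 to Visit 3 for subjects who need two doses. It adds: "Unsolicited AEs occurring after the last visit - and which are not SAE - will be presented in separate listings".
- **Section 4.3.1.2.4 (28-day rule).** For unsolicited non-serious AEs, those analysed within 28 days "correspond to AEs with a time of onset between 0 and 28 days after vaccination or missing". Events that start before vaccination or "with a time of onset higher than 28 days will not be included in analysis but will be listed separately".

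The endpoint in Section 4.2.2 is "Occurrence of unsolicited (spontaneously reported) AEs within 28 days following each / any injection". Section 3.2 (collection of safety data) and Section 5.1.2.2 (methods) also use 0 to 28 days after each injection.

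Visits are not fixed to day 28. Table 3.2 places Visit 2 for subjects aged 9 years or older at "Visit 1 + 28 days" with a window of ± 2 days. Table 3.1 gives the same window for Visit 2 (28 days after Visit 1) and Visit 3 (28 days after Visit 2) in subjects aged 6 months to 8 years.

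The SAP does not say which rule takes precedence, or that an event must meet both.

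**The concern.** If every visit fell exactly on day 28, the two rules would select the same events. The visit window means they need not. When a visit is early or late, the same non-serious event can be in the analysis under one section and in a listing under the other. Both texts are worded as statements of what is analysed, so neither can be dismissed as a mere display convention.

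Describing safety is one of the trial's two objectives, and unsolicited AEs within 28 days are one of four safety endpoints. A plan should yield one numerator from one dataset. Here two programmers could each follow a section literally and count differently. The onset display would not expose it, because its last dated category is open-ended from D8.

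**Working it through.** The plan gives no figure to reproduce on this point. The check lists which onset days each rule admits.

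**Inputs**
- Visit rule: Section 4.3. The visit day itself is taken as inside the interval (an assumption; the text does not say).
- 28-day rule: Section 4.3.1.2.4, with onset = AE start date − date of last vaccination.
- Visit timing: 28 ± 2 days, so D26 to D30 (Tables 3.1 and 3.2).
- Two-dose children: an AE starting on or after the day of dose 2 is counted from dose 2 (by start date; Section 4.3.1.2.3 uses the visit number first where there is one).

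**One-dose subjects (9 years or older).** With Visit 2 on day v, the visit rule admits D0 to Dv and the 28-day rule admits D0 to D28. They differ on |v − 28| onset days.

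| Visit 2 | Analysed by visit rule only | Analysed by 28-day rule only |
|---|---|---|
| D26 | none | D27, D28 |
| D27 | none | D28 |
| D28 | none | none |
| D29 | D29 | none |
| D30 | D29, D30 | none |

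**Two-dose subjects (6 months to 8 years).** Days are counted from dose 1.

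| Visit 2 | Visit 3, days after Visit 2 | Visit rule only | 28-day rule only |
|---|---|---|---|
| D26 | 26 | none | 53, 54 |
| D26 | 28 | none | none |
| D26 | 30 | 55, 56 | none |
| D28 | 26 | none | 55, 56 |
| D28 | 28 | none | none |
| D28 | 30 | 57, 58 | none |
| D30 | 26 | 29 | 57, 58 |
| D30 | 28 | 29 | none |
| D30 | 30 | 29, 59, 60 | none |

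Reading the second table:
- Around Visit 3 the pattern is that of the one-dose subjects. For example, days 53 and 54 with dose 2 on D26 are 53 − 26 = 27 and 54 − 26 = 28 days after dose 2.
- A late Visit 2 (D30) adds one disputed day, D29, before dose 2 is given. D30 itself becomes day 0 after dose 2.
- An early Visit 2 (D26) creates no disputed day. An AE on D27 lies between Visits 2 and 3 under one rule and one day after dose 2 under the other, so both analyse it.

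**Size.** For in-window visits, at most 2 onset days are disputed per vaccination. A two-dose child with both visits off schedule can reach 1 + 2 = 3 in all. Two days are 2/28 = 7% of the follow-up time after a dose. In a group of 100, one subject whose status changes moves the percentage by 1/100 = 1 point.

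**Out-of-window visits.** The difference grows day for day with |v − 28|. Section 5.2.2 excludes subjects with out-of-window sampling or second vaccination from the PPAS. The safety analysis uses the SafAS (5.2.3), which asks only for one dose, so those subjects stay in.

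**The case against.** The strongest reply is that Section 4.3 only introduces terms, while Section 4.3.1.2.4 is the dedicated derivation and defines the 28-day tables explicitly. With the endpoint and methods also at 28 days, a careful programmer would follow it and list D29 and D30 events. That is the likely outcome, and it limits the practical risk. It does not remove the contradiction. Section 4.3 says what is to be analysed, and the note in 4.3.1.2.4 removes later events from analysis altogether, not just from one table. Nor can the 28-day set be read as a subset of the visit set: after an early final visit, 4.3 takes D27 and D28 out while 4.3.1.2.4 keeps them in.

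A second reply is that the early-visit case is largely theoretical. At the final visit the diary card is collected, AEs are recorded and the termination record is completed, and no later collection of non-serious AEs is scheduled. This stands. Such an event reaches the database only if reported outside the schedule, and no rewording recovers one that is never reported.

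A third reply is that no effect on a result has been shown. This also stands. A subject's status changes only if the visit is off day 28, an AE starts in the one- or two-day edge, and the subject has no other counted unsolicited AE. The analysis is descriptive, with no hypothesis tested (5.1.2.1).

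**Conclusion.** The contradiction is real, and it concerns unsolicited non-serious AEs. The rules conflict in three situations: onset on D29 or D30 when the final visit is late; onset on D29 before dose 2 when Visit 2 is late in two-dose children; and a reported onset on D27 or D28 after an early final visit. The visit rule in 4.3 is the one out of line with the rest of the plan. For in-window visits the effect is at most 2 onset days per vaccination, probably few events, and more if a visit is out of window. This rests on the visit day counting as inside the interval and on start dates fixing the last vaccination.

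A reader might infer more, but the document does not support it:
- *That SAEs are affected in the same way.* The exclusion in 4.3.1.2.4 covers only non-serious AEs. Section 4.3 exempts SAEs from the listing after the last visit, and 4.3.1.3.3 also analyses SAEs over the whole study.
- *That each dose loses or gains up to 2 days on both sides of day 28.* Around dose 2 an early visit costs nothing and a late one disputes a single day.
- *That reported rates could shift by 7%.* That figure is a share of follow-up time, not a change in a rate.
- *That both rules apply jointly, giving each subject a different window under the 28-day label.* The SAP never says so, and it would contradict the inclusion text of each section.

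**What to change.** In Section 4.3, replace the selection sentence with: *Unsolicited non-serious AEs analysed are those with onset 0 to 28 days after the last preceding vaccination, or with missing onset, as in 4.3.1.2.4; all others are listed separately.* The sentence that follows, on non-serious events after the last visit, should go with it. If it stays, the conflict over D27 and D28 stays too. Leave the SAE rules in 4.3.1.3.3 unchanged. No separate sentence closing the post-dose-1 window is needed, because counting onset from the last vaccination (4.3.1.2.3 and 4.3.1.2.4) already does that.

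The cost is one or two sentences in the SAP, with no new data and no change to the endpoint.
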